7.3.3 Safety analyses

Safety will be assessed for the endpoints listed in [Section 5.2.1](#). All treated subjects (that is, all subjects who received at least one dose of study drug), will be included in the safety analysis. Safety analyses will be descriptive in nature and will be based on BI standards. No hypothesis testing is planned.

Treatments will be compared in a descriptive way. The placebo control group in the safety evaluation will consist of all placebo treated subjects, regardless of the dose group in which they were treated. The active treatment groups will be compared to the placebo group in a descriptive way. Tabulations of frequencies/proportions will be used for the evaluation of categorical (qualitative) data, and tabulations of descriptive statistics will be used to analyse continuous (quantitative) data.

The analyses will be done by 'treatment at onset'.

Measurements (such as ECG, vital signs, or laboratory parameters) or AEs will be assigned to treatments (see [Section 4.1](#)) based on the actual treatment at the planned time of the measurement or on the recorded time of AE onset (concept of treatment emergent AEs). Therefore, measurements planned or AEs recorded prior to first intake of trial medication will be assigned to 'screening', those between first trial medication intake until the end of trial visit will be assigned to the treatment period, and those after the end of trial examination will be assigned to 'post-study'. These assignments including the corresponding time intervals will be defined in detail in the TSAP.

Additionally, further treatment intervals (analysing treatments) may be defined in order to provide summary statistics for time intervals, such as combined treatments, on-treatment totals or periods without treatment effects (such as screening and post-study intervals).

Adverse events will be coded using the Medical Dictionary for Regulatory Activities (MedDRA). Frequency, severity and causal relationship of AEs will be tabulated by treatment, system organ class and preferred term. SAEs, AESIs (see [Section 5.2.2.1](#)) and other significant AEs (according to ICH E3) will be listed separately.

Laboratory data will be compared to their reference ranges. Values outside the reference range as well as values defined as clinically relevant will be highlighted in the listings. Additionally, differences from baseline will be evaluated.

Proprietary confidential information © 2017 Boehringer Ingelheim International GmbH or one or more of its affiliated companies

Vital signs or other safety-relevant data observed at screening, baseline, during the course of the trial and at the end-of-trial evaluation will be assessed with regard to possible changes compared to findings before start of treatment.

A centralised evaluation of all 12-lead ECGs recordings (see [Section 5.2.4](#)) will be the basis for the derivation of further ECG parameters based on the ECG variables QT, HR, QTcF, QTcB, PR, QRS, and RR. The baseline value of an ECG variable is defined as the mean of the triple ECG measurements prior to drug administration. The derivation of the quantitative and qualitative ECG endpoints and their analyses will be described in the TSAP.

7.3.4 Preliminary PK analyses

A preliminary analysis of PK parameters (AUC_{0-168} and C_{max} of BI 473494), provided as individual values and geometric means of at least the first 2 cohorts per dose level, will be performed for

- all dose levels up to n-2 before proceeding to dose level n (with $n \leq 1.6$ mg)
- all dose levels up to n-1 before proceeding to dose level n (with $n > 1.6$ mg)

(Note: Data from the first two cohorts of the above mentioned dose levels will be sufficient as long as the data from at least 2 subjects on active were available)

No inferential statistical interim analysis is planned. However, after each dose group the investigator (or deputy) is allowed to postpone further dose progression until a preliminary analysis of the data already obtained has been performed

7.3.5 Pharmacokinetic analyses

The pharmacokinetic parameters listed in [Section 5.5.1](#) for drug BI 473494 will be calculated according to the BI SOP ‘Standards and processes for analyses performed within Clinical Pharmacokinetics/Pharmacodynamics’ ([001-MCS-36-472](#)).

Subjects who are not included in the PKS (refer to [Section 7.3.2](#)) will be reported with their individual plasma / urine concentrations and individual pharmacokinetic parameters;

Proprietary confidential information © 2017 Boehringer Ingelheim International GmbH or one or more of its affiliated companies

however, they will not be included in descriptive statistics for plasma / urine concentrations, pharmacokinetic parameters.

Only concentration values within the validated concentration range and actual sampling times will be used for the calculation of pharmacokinetic parameters. Concentrations used in the pharmacokinetic calculations will be in the same format provided in the bioanalytical report, (that is, to the same number of decimal places provided in the bioanalytical report).

If a predose concentration value is greater than 5% of C_{max} , the subject's pharmacokinetic data will be not included in any statistical evaluations, in accordance with international guidances. The individual pharmacokinetic parameters of such a subject will be calculated and listed separately. If a predose concentration is above BLQ, but less than or equal to 5% of the subject's C_{max} value, the subject's data without any adjustments will be included in all pharmacokinetic measurements and calculations.

Point estimates and 95% CIs will be provided for the secondary endpoints (cf. [Section 5.5.1.1](#)). The secondary endpoints will be log-transformed prior to fitting the ANCOVA model (cf. [Section 7.3.2](#)).

The following descriptive statistics will be calculated for all PK parameters

N, arithmetic mean, standard deviation, minimum, median, maximum, arithmetic coefficient of variation, geometric mean, and geometric coefficient of variation. The data format for descriptive statistics of concentrations will be identical with the data format of the respective concentrations. The descriptive statistics of PK parameters will be calculated using the individual values with the number of decimal places as provided by the evaluation program. Then the individual values as well as the descriptive statistics will be reported with 3 significant digits in the clinical trial report.

In addition to the non-compartmental analysis, a population pharmacokinetic analysis will be performed. This population pharmacokinetic analysis will not be part of the CTR, but will be reported separately.

More details will be provided in the TSAP.

7.4 HANDLING OF MISSING DATA

7.4.1 Safety

With respect to safety evaluations, it is not planned to impute missing values.

7.4.2 Plasma/urine drug concentration - time profiles

Handling of missing PK data will be performed according to the relevant SOP of the Sponsor ([001-MCS-36-472](#)).

Drug concentration data identified with NOS (no sample available), NOR (no valid result), NOA (not analysed), BLQ (below the lower limit of quantification), or NOP (no peak detectable) will be displayed as such and not replaced by zero at any time point (this rule also applies also to the lag phase, including the predose values).

7.4.3 Pharmacokinetic parameters

Handling of missing PK data will be performed according to the relevant SOP of the Sponsor ([001-MCS-36-472](#)).

For the non-compartmental analysis, concentration data identified with NOS, NOR or NOA will generally not be considered. Concentration values in the lag phase identified as BLQ or NOP will be set to zero. All other BLQ/NOP values of the profile will be ignored. The lag phase is defined as the period between time zero and the first time point with a concentration above the quantification limit.

7.5 RANDOMISATION

Each dose group will be divided into three cohorts. The subjects of the first two cohorts will not be randomised to maintain a treatment sequence of 'active-placebo' in cohort 1 and 'active-active' in cohort 2 due to safety reasons. In the third cohort of each dose level the subjects will be assigned to active or placebo treatment using a 3:1 allocation ratio.

The sponsor will arrange for the randomisation as well as packaging and labelling of trial medication. The randomisation list will be generated using a validated system, which involves a pseudo-random number generator and a supplied seed number so that the resulting allocation is both reproducible and non-predictable.

The randomisation list will contain additional blocks to allow for subject replacement (refer to [Section 3.3.5](#)).

7.6 DETERMINATION OF SAMPLE SIZE

It is planned to include a total of 88 subjects in this trial. The planned sample size is not based on a power calculation. The size of 8 subjects per dose group (6 on active treatment, and 2 on placebo) is commonly used in single-rising dose studies of the present type and is in general considered as sufficient for the exploratory evaluation of single dose safety and pharmacokinetics [[R95-0013](#)].

Additional subjects may be entered to allow testing of additional doses on the basis of experience gained during the trial conduct (e.g. preliminary PK data), provided the planned and approved highest dose will not be exceeded. Thus, the actual number of subjects entered may exceed 88, but will not exceed 104 subjects entered.

8. INFORMED CONSENT, DATA PROTECTION, TRIAL RECORDS

The trial will be carried out in compliance with the protocol, the principles laid down in the Declaration of Helsinki, in accordance with the ICH Harmonised Tripartite Guideline for Good Clinical Practice (GCP) and relevant BI SOPs.

The Investigator should inform the Sponsor immediately of any urgent safety measures taken to protect the study subjects against any immediate hazard, and also of any serious breaches of the protocol or of ICH GCP.

The rights of the Investigator and of the Sponsor with regard to publication of the results of this trial are described in a separate agreement between the Investigator or the trial site and the Sponsor. As a general rule, no trial results should be published prior to finalisation of the CTR.

Insurance Coverage: The terms and conditions of the insurance coverage must be given to each subject and are made available to the investigator via documentation in the ISF.

8.1 STUDY APPROVAL, SUBJECT INFORMATION, AND INFORMED CONSENT

This trial will be initiated only after all required legal documentation has been reviewed and approved by the respective Institutional Review Board (IRB) / Independent Ethics Committee (IEC) and competent authority (CA) according to national and international regulations. The same applies for the implementation of changes introduced by amendments.

Prior to a subject's participation in the trial, written informed consent must be obtained from each subject (or the subject's legally accepted representative) according to ICH GCP and to the regulatory and legal requirements of the participating country. Each signature must be personally dated by each signatory and the informed consent and any additional subject information form are to be retained by the investigator as part of the trial records. A copy of the signed and dated written informed consent and any additional subject information must be given to each subject or the subject's legally accepted representative.

The subject must be informed that his/her personal trial-related data will be used by Boehringer Ingelheim in accordance with the local data protection law. The level of disclosure must also be explained to the subject.

The subject must be informed that his or her medical records may be examined by authorised monitors (Clinical Monitor Local/Clinical Research Associate) or Clinical Quality Assurance auditors appointed by Boehringer Ingelheim, by appropriate IRB/IEC members, and by inspectors from regulatory authorities.

8.2 DATA QUALITY ASSURANCE

A quality assurance audit/inspection of this trial may be conducted by the Sponsor or Sponsor's designees, by IRBs/IECs, or by regulatory authorities. The quality assurance auditor will have access to all medical records, the investigator's trial-related files and correspondence, and the informed consent documentation of this clinical trial.

Proprietary confidential information © 2017 Boehringer Ingelheim International GmbH or one or more of its affiliated companies

The data management procedures to ensure the quality of the data are described in detail in the trial data management and analysis plan (TDMAP) available in the TMF.

8.3 RECORDS

CRFs for individual subjects will be provided by the Sponsor. For drug accountability, refer to [Section 4.1.9](#).

8.3.1 Source documents

Source documents provide evidence for the existence of the subject and substantiate the integrity of the data collected. Source documents are filed at the investigator's site.

All data reported in the CRFs must be consistent with the source data or the discrepancies must be explained.

The investigator may need to request previous medical records or transfer records, depending on the trial.

8.3.2 Direct access to source data and documents

The investigator/institution will permit trial-related monitoring, audits, IRB/IEC review and regulatory inspection, providing direct access to all related source data/documents. CRFs and all source documents, including progress notes (if applicable) and copies of laboratory and medical test results must be available at all times for review by the sponsor's clinical trial monitor, auditor and inspection by health authorities (e.g. FDA). The Clinical Research Associate/on site monitor and auditor may review all CRFs, and written informed consents. The accuracy of the data will be verified by reviewing the documents described in [Section 8.3.1](#).

8.3.3 Storage period of records

Trial site:

The trial site must retain the source and essential documents (including ISF) according to the national or local requirements (whatever is longer) valid at the time of the end of the trial.

Sponsor:

The Sponsor must retain the essential documents according to the Sponsor's SOPs.

8.4 EXPEDITED REPORTING OF ADVERSE EVENTS

BI is responsible to fulfil their legal and regulatory reporting obligation in accordance with regulatory requirements.

8.6 COMPLETION OF TRIAL

The EC/competent authority in each participating EU member state needs to be notified about the end of the trial (last subject/subject out, unless specified differently in [Section 6.2.4](#) of the CTP) or early termination of the trial.

10. APPENDICES

Not applicable.

Proprietary confidential information © 2017 Boehringer Ingelheim International GmbH or one or more of its affiliated companies

2. LIST OF ABBREVIATIONS

Term	Definition / description
ADA	Anti-drug Antibody
ADS	Analysis Dataset
AE	Adverse Event
AESI	Adverse Event of Special Interest
ALT	Alanine Aminotransferase
ANCOVA	Analysis of Covariance
ANOVA	Analysis of Variance
AST	Aspartate Aminotransferase
AUC	Area Under The Concentration-Time Curve
AUC _{0-tz}	Area under the concentration-time curve of the analyte in plasma over the time interval from 0 to the last quantifiable data point

BI	Boehringer Ingelheim
CARE	Clinical Analysis and Reporting Environment
CI	Confidence Interval
C _{max}	Maximum measured concentration of the analyte in plasma
CRF	Case report form
CTP	Clinical Trial Protocol
CTR	Clinical Trial Report
CV	Arithmetic Coefficient of Variation
DB	Dose Proportionality, Between-Subject Design
DBLM	Database Lock Meeting
DILI	Drug induced liver injury
ECG	Electrocardiogram
EudraCT	European Union Drug Regulating Authorities Clinical Trials

Term	Definition / description
gCV	Geometric Coefficient of Variation
gMean	Geometric Mean
HR	Heart Rate
ICH	International Conference On Harmonisation
ISF	Investigators Site File
iPD	Important Protocol Deviation
LLT	Lower Level Term
Max	Maximum
MedDRA	Medical Dictionary For Regulatory Activities
Min	Minimum
N	Number non-missing observations
O*C	Oracle Clinical
P10	10th percentile
P90	90th percentile
PD	Pharmacodynamics
PDS	Pharmacodynamic Analysis Set
PK	Pharmacokinetics
PKS	PK Parameter Analysis Set
PR	Pulse Rate
PT	Preferred Term
Q1	1st quartile
Q3	3rd quartile
QRS	Complex of three closely related waves on the ECG (Q, R and S wave)
QT	Time between start of the Q-wave and the end of the T-wave on the ECG
QTc	QT interval corrected for heart rate using the method of Fridericia (QTcF) or Bazett (QTcB)
RAGe	Report Appendix Generator system
REP	Residual Effect Period
RPM	Report Planning Meeting
SAS®	Statistical Analysis System

Term	Definition / description
SD	Standard Deviation
SOC	System Organ Class
TMCP	Translational Medicine and Clinical Pharmacology
TS	Treated Set
TSAP	Trial Statistical Analysis Plan
ULN	Upper Limit of Normal
WHO-DD	World Health Organization Drug Dictionary
XPKISTAT	Library of SAS [®] Macros for PK analysis

3. INTRODUCTION

As per ICH E9 (1), the purpose of this document is to provide a more technical and detailed elaboration of the principal features of the analysis described in the protocol, and to include detailed procedures for executing the statistical analysis of the primary and secondary variables and other data.

This trial statistical analysis plan (TSAP) assumes familiarity with the Clinical Trial Protocol (CTP), including Protocol Amendments. In particular, the TSAP is based on the planned analysis specification as written in CTP Section 7 “Statistical Methods and Determination of Sample Size”. Therefore, TSAP readers may consult the CTP for more background information on the study, e.g., on study objectives, study design and population, treatments, definition of measurements and variables, planning of sample size, randomisation.

Study data will be stored in a trial database within the Oracle ClinicalTM (O*C) system.

Pharmacokinetic (PK) parameters will be calculated using Phoenix WinNonlin™ software (version 6.3, Certara USA Inc., Princeton, NJ, USA).

The statistical analyses will be performed within the validated Clinical Analysis and Reporting Environment (CARE), including SAS™ (current Version 9.4, by SAS Institute Inc., Cary, NC, USA), and a number of SAS™-based tools (e.g., macros for the analyses of AE data or laboratory data; Report Appendix Generator system (RAGe) for compilation/formatting of the Clinical trial Report (CTR) appendices).

4. CHANGES IN THE PLANNED ANALYSIS OF THE STUDY

All analyses described in the TSAP are outlined in the CTP. The following changes compared to the protocol will be made:

Dose escalation was stopped after the second dose group (75 µg BI 473494). Therefore, all analyses will be performed for the first and second dose group only.

- As there are only two dose groups available, no dose proportionality analysis will be done. Secondary endpoints (AUC_{0-tz} and C_{max} of BI 473494) will be analysed descriptively only.

- As there are only two dose groups available and only little exposure levels expected, no ECG exposure-response analyses will be done.

As an abbreviated CTR will be written, the change from baseline in body weight will be analysed descriptively only.

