7. STATISTICAL METHODS AND DETERMINATION OF SAMPLE SIZE

7.1 STATISTICAL DESIGN – MODEL

7.1.1 Objectives

The primary objective of this trial is to investigate the safety and tolerability of BI 473494 by using descriptive statistics for all endpoints comparing active dose groups to placebo. The primary endpoint is defined in [Section 5.2.1](#). Inferential statistics is not planned (as explained in [Section 7.2](#)).

The secondary objective is the exploration of the PK of BI 473494. Endpoints as specified in [Sections 5.5.1](#) and [5.7.1](#) will be analysed by descriptive statistics. Secondary endpoints as defined in [Section 5.5.1.1](#), as well as AUC_{0-168} and $AUC_{0-\infty}$, will be subjected to analysis of dose proportionality by use of the power model.

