7.2 NULL AND ALTERNATIVE HYPOTHESES

Safety and tolerability of different dose groups of BI 473494 are to be determined on the basis of the investigated parameters in comparison to placebo. It is not planned to test any statistical hypotheses with regard to these variables in a confirmatory sense. Instead, they will be described in their entirety and evaluated by descriptive statistical methods.

Confidence intervals will be computed and will have to be interpreted in the perspective of the exploratory character of the study, i.e. confidence intervals are considered as interval estimates for effects.

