The following total will be provided in addition (Section 15.3 only):

- a total over all BI 473494 treated phases ("**BI Total**")
- a total over all on treatment phases included in this analysis ("**Total on treatment**") (Section 15.3 only)

B) Section 15.4 and Appendix 16.1.13.1.8 (except for ClinicalTrials.gov and EudraCT) of the CTR displays:

- Screening
- On treatment (labelled with the name of the study treatment (short label))

In Section 16.1.13.1.8 AE tables, the following totals will be provided in addition:

- a total over all BI 473494 treated phases ("**BI Total**")
- a total over all study phases ("**Total**")

Tables of vital signs and laboratory values will present results by the above mentioned on treatment phase.

For detailed information on the handling of the treatments in the O*C views refer to Technical TSAP ADS (analysis data set) plan and Analysis Data Reviewers guide.

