7. PLANNED ANALYSIS

The placebo group in the safety evaluation will consist of all placebo treated subjects, regardless of the dose group in which they were treated.

Safety analysis (refer to [Section 7.8](#)) will be performed by and will be presented in Sections 15.1 to 15.4 of the CTR and in Appendix 16.2 and 16.1.13.1.

Descriptive data analysis of PK parameters and concentrations will be performed by the department Translational Medicine and Clinical Pharmacology (TMCP) at BI and will be presented in Section 15.6 and 15.7 of the CTR.

The format of the listings and tables will follow the standards defined in the BI corporate guideline “Reporting of Clinical Trials and Project Summaries” [001-MCG-159] ([6](#)) with the exception of those generated for PK-calculations.

The individual values of all subjects will be listed, sorted by treatment group, subject number, and visit.

The listings will be included in Appendix 16.2 of the CTR.

For end-of-text tables, the set of summary statistics for non-PK parameters is:

N	number non-missing observations
Mean	arithmetic mean
SD	standard deviation
Min	minimum
Median	median
Max	maximum

For analyte concentrations, the following descriptive statistics will additionally be calculated:

CV	arithmetic coefficient of variation
gMean	geometric mean
gCV	geometric coefficient of variation

For PK parameters, the following descriptive statistics will additionally be calculated:

CV	arithmetic coefficient of variation
gMean	geometric mean
gCV	geometric coefficient of variation
P10	10th percentile
Q1	1st quartile
Q3	3rd quartile
P90	90th percentile

The data format for descriptive statistics of concentrations will be identical with the data format of the respective concentrations. The descriptive statistics of PK parameters will be calculated using the individual values with the number of decimal places as provided by the evaluation program. Then the individual values as well as the descriptive statistics will be reported with three significant digits in the CTR.

Tabulations of frequencies for categorical data will include all possible categories and will display the number of observations in a category, as well as the percentage (%) for each treatment group. Percentages will be rounded to one decimal place and will be based on all subjects in the respective subject set whether they have non-missing values or not. The category 'missing' will be displayed only if there are actually missing values.

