7.8.1 Adverse events

AEs will be coded with the most recent version of MedDRA.

The analyses of AEs will be descriptive in nature and will be based on BI standards as presented in the corporate guideline: “Analysis and Presentation of Adverse Event Data from Clinical Trials” [001-MCG-156] ([8](#)).

The standard AE analyses will be based on the number of subjects with AEs (and not on the number of AEs).

For analysis multiple AE occurrence data on the CRF will be collapsed into an AE provided that all of the following applies:

- All AE attributes are identical (LLT, intensity, action taken, therapy required, seriousness, reason for seriousness, relationship, outcome, AE of special interest)
- The occurrences were time-overlapping or time-adjacent (time-adjacency of two occurrences is given if the second occurrence started within one hour after end of the first occurrence).

For further details on summarization of AE data, please refer to [001-MCG-156] ([8,4](#)).

Section 5.2.2.1 of the CTP: *The following are considered as AESIs in this trial:*

- *Hepatic injury: A hepatic injury is defined by the following alterations of hepatic laboratory parameters:*
 - *an elevation of AST (aspartate aminotransferase) and/or ALT (alanine aminotransferase) ≥ 3 -fold ULN combined with an elevation of total bilirubin ≥ 2 -fold ULN measured in the same blood sample, and/or*

- aminotransferase (ALT, and/or AST) elevations ≥ 10 fold ULN

These lab findings constitute a hepatic injury alert and the patients showing these lab abnormalities need to be followed up according to the 'DILI checklist' provided in the ISF. In case of clinical symptoms of hepatic injury (icterus, unexplained encephalopathy, unexplained coagulopathy, right upper quadrant abdominal pain, etc.) without lab results (ALT, AST, total bilirubin) available, the Investigator should make sure these parameters are analysed, if necessary in an unscheduled blood test. Should the results meet the criteria of hepatic injury alert, the procedures described in the DILI checklist should be followed.

The analysis of adverse events will be based on the concept of treatment emergent adverse events.

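### Does the SAP need confidence intervals for the primary endpoint because Protocol 7.2 says intervals will be computed?

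*SAP*

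**What the plan says.** Protocol 7.2 deals with safety and tolerability in comparison with placebo. It rules out confirmatory testing, says these variables will be evaluated descriptively, and then adds: "Confidence intervals will be computed and will have to be interpreted in the perspective of the exploratory character of the study". It names no endpoint, confidence level or method.

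Other protocol sections are more specific:

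- On the primary objective, 7.1.1 says "Inferential statistics is not planned".
- Section 5.2.1 defines the primary endpoint as a count with a percentage, and 7.3.3 plans frequency tables for categorical safety data.
- Section 7.3.2 plans a two-sided 95% interval for the dose-proportionality slope.
- Section 7.3.5 says "Point estimates and 95% CIs will be provided for the secondary endpoints". Its next sentence concerns the log transformation before the regression of 7.3.2 is fitted.

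SAP 4 begins "All analyses described in the TSAP are outlined in the CTP. The following changes compared to the protocol will be made". It drops dose proportionality, limits AUC0-tz and Cmax to description, drops the ECG exposure-response analysis and limits body-weight change to description. It does not mention the general statement in 7.2.

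Under SAP 7, categorical tables "will display the number of observations in a category, as well as the percentage (%) for each treatment group". The list headed "For PK parameters, the following descriptive statistics will additionally be calculated" adds coefficients of variation, the geometric mean, quartiles and percentiles, but no interval. SAP 7.8.1 says "The standard AE analyses will be based on the number of subjects with AEs", and SAP 6.1 adds a BI Total column, "a total over all BI 473494 treated phases". In the public SAP text, CI occurs only in the list of abbreviations.

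**The concern.** The SAP is meant to turn Section 7 of the protocol into procedures and to list departures from it. A sentence in Section 7 says that intervals will be computed. The public SAP neither specifies them nor lists their removal, so a reader cannot tell whether they were dropped on purpose or overlooked.

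The early stop makes this look worse. With 6 subjects per dose and 4 on pooled placebo, one subject moves a percentage by 16.7 or 25.0 points, yet SAP 7 reports percentages to one decimal. An observed 0% of subjects with drug-related adverse events could be taken as evidence of good tolerability when it excludes very little. The endpoint at stake is the primary one.

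**Working it through.** **1. Group sizes.** Inputs: 11 dose groups of 6 active and 2 placebo (Protocol 3.1, 7.6). The planned total reproduces: 11 × (6 + 2) = 88. The ceiling is 13 × 8 = 104. Escalation stopped after two groups (SAP 4) and placebo is pooled (SAP 6.1, 7), so the planned numbers become 6 and 6 active (BI Total 2 × 6 = 12) and 2 × 2 = 4 placebo. The full design would have given 66 and 22. The documents do not give the numbers actually treated.

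**2. What intervals per group would show.** Exact (Clopper-Pearson) 95% limits. For zero events the upper limit is 1 − 0.025^(1/n). For 0 < x < n the limits are the 2.5% quantile of Beta(x, n − x + 1) and the 97.5% quantile of Beta(x + 1, n − x). Event counts are illustrative, as the documents give none.

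| Events / n | Observed | Exact 95% limits |
|---|---|---|
| 0/6 | 0.0% | 0 to 45.9% |
| 1/6 | 16.7% | 0.4 to 64.1% |
| 3/6 | 50.0% | 11.8 to 88.2% |
| 0/12 | 0.0% | 0 to 26.5% |
| 1/12 | 8.3% | 0.2 to 38.5% |
| 0/4 | 0.0% | 0 to 60.2% |
| 1/4 | 25.0% | 0.6 to 80.6% |

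Each row needs only the count and n. The count is in the planned tables, and n can be read from the treatment group or recovered from the count and its percentage whenever the count is not zero.

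**3. What intervals for effects would show.** Protocol 7.2 speaks of effects, in a section about comparison with placebo. That means differences between groups, not single proportions. Newcombe 95% intervals for the difference in percentage points:

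- 0/6 against 0/4: 0.0 (−49.0 to 39.0)
- 3/6 against 1/4: 25.0 (−29.7 to 62.3)
- 3/6 against 0/4: 50.0 (−8.1 to 81.2)

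The widths are 88.0, 92.0 and 89.3 points. All three include zero.

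**4. Where each interval in the protocol went.**

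| Protocol statement | Target named? | Fate in the SAP |
|---|---|---|
| 7.3.2, slope | Yes | Dropped openly in SAP 4 with dose proportionality |
| 7.3.5, secondary endpoints | Yes, AUC0-tz and Cmax | In effect withdrawn: SAP 4 limits both to description |
| 7.2, general sentence | No | Not mentioned |
| 5.2.1 and 7.3.3, primary endpoint | No interval planned | Count and percentage, as in the protocol |

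Every interval with a named target is accounted for. The count-and-percentage display of the primary endpoint was set by the protocol and does not result from an omission in the SAP.

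**The case for a change.** The strongest case for acting is that 7.2 says intervals will be computed, not that they may be. The sentence comes straight after a paragraph on safety, and SAP 4 presents itself as the list of changes. The statement in 7.1.1 does not cancel it, because an interval labelled descriptive is compatible with having no inference. The fix would be cheap: a few lines of code or one sentence.

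Part of this stands. SAP 4 does not dispose of the general sentence, and the zero-event limits show how little an observed 0% excludes.

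The rest does not carry it to a change. The sentence mainly tells the reader how to interpret intervals, and it gives the analyst no endpoint, level or method to carry out. It may have been written for material that is not public: Protocol 7.1.1 refers to a Section 5.7.1 that is absent from the text, the public SAP skips 6.4, 7.6 and 9, and the sponsor's adverse-event standard is not reproduced. A broken commitment therefore cannot be established from what is visible. Exact limits for each group would also not be the intervals for effects that 7.2 describes. They would be a preferred display, not delivery of the promise.

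**Conclusion.** No change to the plan follows. Carried out as written, it gives sound descriptive counts for a trial with no power calculation, no planned test and, after the stop, 16 planned subjects in the analysis. The tables carry counts, individual data are listed, and the limits in the working (for example 0 to 45.9% for 0/6) follow directly from what is shown. Intervals for differences from placebo would be about 90 points wide in the illustrated cases and would support no firmer conclusion. A note in SAP 4 about the 7.2 sentence would tidy the record but would change no result, decision or conclusion.

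This rests on three assumptions: that the treated numbers are close to the planned 6, 6 and 4; that the hidden sections hold no separate interval commitment for the primary endpoint; and that the report reads a 0% in a group of 6 as the small-sample finding it is.
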